1.0 Protocol Summary

The purpose of this study is to investigate a targeted approach for the management of the plantar lesions of epidermolysis bullosa simplex (EBS). The drug to be tested is called sirolimus (Rapamycin), it is a mammalian Target of Rapamycin (mTOR) inhibitor to be used as a topical agent for treatment of the blistering/callus lesions on the soles of feet.

Sirolimus 2% ointment, has been shown to reduce expression of keratin (KRT) 6/16 and improve walking ability in a related condition affecting the feet, pachyonychia congenita, as well as being safe. Since sirolimus may have similar effects on the paired KRT 5/14 which are affected in EBS, we are conducting a prospective, double-blind, randomized, placebo-controlled, crossover study.

Participants will be assigned to treat both feet with either topical sirolimus 2% ointment twice daily or placebo (vehicle-control) for 12 weeks followed by a washout period of four weeks, then retreatment to both feet with the switched intervention followed by a washout period of four weeks, and then a post-study phone call at 8 weeks thereafter.

This study will exploit the naturally occurring transcriptional regulation of keratin sequences, the known gene aberration causing EBS, and assess the potential for mTOR pathway inhibition in treatment of EB patient's plantar lesions.

2.0 Background and Rationale

2.1 Disease background

Epidermolysis bullosa (EB) represents a spectrum of conditions characterized by blistering and mechanical fragility of the skin. Individuals with EB display tremendous clinical diversity, as the dermal-epidermal basement membrane zone contains a number of specialized adhesive structures that link the basal epidermis cytoskeleton to the papillary dermis. The molecular basis of EB has been linked to 18 genes, leading to the classification of 28 clinical (15 EBS, 8 JEB, 14 DEB, 1 Kindler)

EB subtypes and four major EB groups (Fine et al., 2014). With importance to this proposal, the EB simplex (EBS) subtype has been well-characterized genetically, and it is this characterization the authors plan to exploit with the goal of improving current state of the art.

EBS refers to a group of rare inherited disorders caused by blister formation within the epidermis. The clinical features of all forms of EBS manifest with skin

blistering. Palmoplantar-keratoderma, nail dystrophy and shedding, alopecia and oral involvement can be seen. Excruciating pain and severe impairment in quality of life in EBS patients has been reported (Fine et al., Clin Exp Dermatol 2004). Causes of early mortality in EBS patients include infections and protein loss leading to malnutrition, fluid and electrolyte imbalances, and anemia. Patient care has been limited to supportive measures, including wound care, nutritional support, and antibiotics. In 1991, two groups published in Cell and Science independently revealing the first keratin disorder with a genetic basis in humans, EBS. EBS is usually caused by missense mutations in the genes encoding keratin 5 and 14 (KRT5 and KRT14, respectively) leading to a dominant negative effect on the function of normal keratins (Lane et al., J Pathol 2004), resulting in keratin cytoskeleton dysfunction. The prevalence is estimated to be 6 to 30 per 1 million live births.

2.2 Sirolimus

Sirolimus binds to immunophilin FK506 binding protein-12 and creates a complex that inhibits the activation of mTORC1 that leads to decreased translational initiation. Consequently, sirolimus has shown to decrease overall protein synthesis by 20% and cause cell cycle arrest in G1 phase. (Castedo et al., 2001) Other effects of sirolimus include apoptosis, inhibition of T-cell activation and reduced expression of specific proteins involved in angiogenesis and lymphangiogenesis, specifically hypoxia inducible factor-1a (HIF-1a) and vascular endothelial growth factor (VEGF). (Guba et. al 2002)

Systemic use of sirolimus is associated with side effects that include opportunistic infection, mucositis, hypercholesterolemia, decreased renal function, elevation in liver transaminases, thrombocytopenia, neutropenia, and delayed wound healing. Minor adverse cutaneous events of systemic therapy include acne like eruptions, edema, and nail disorders. mTOR inhibitors in topical preparations show promise as an ideal delivery system to minimize systemic adverse effects in the treatment of dermatological disease.

Topical formulations of sirolimus are being used off-label in a variety of dermatological diseases (see Table 1) (Fogel et al, 2015). Formulations are mostly crushed sirolimus from tablet compounded with petrolatum to form an ointment, with a few studies utilizing the commercially available oral sirolimus solution (1mg/ml). Most of the topical formulations were found to have no local adverse effects, with irritation being more common using the aqueous solution. In all cases the systemic level of sirolimus was less than 2ng/ml that is below the standard serum levels required for immunosuppression (5-15 ng/ml). Treatment duration and frequency varied according to condition.

2.3 Rationale

The development of new treatment modalities is critical in improving disease state and the quality of life for EBS patients. Disease classification has changed from descriptive to a detailed pathogenesis over the past several decades, and

now scientists are drawn to ask the question, “How can we approach this disease in a targeted fashion?”

Therapeutic approaches targeting the deleterious effects of abnormal and abundant keratins are emerging. Topical sirolimus 2% is one potential medication yet to be utilized in EBS patients. It has been shown to selectively block 5'oligopyrimidine (TOP) mRNA translation thereby altering mRNAs 5'TOP motifs (Raught et al., 2001). Published sequence data suggest KRT5 mRNA, but not KRT14 mRNA, contain the 5'TOP motif (Hickerson et al., 2009) and thus are viable drug targets of mTOR for the treatment of EBS variants.

4.0 Objectives and Scientific aims

Aim 1: To assess the safety of topical sirolimus 2% use in the treatment of plantar lesions in epidermolysis bullosa simplex (EBS).

Aim 2: To assess the efficacy of topical sirolimus 2% to improve the clinical severity of lesional skin, including pain and itch symptoms.

Aim 3: To assess improvement in walking ability.

5.0 Criteria for Subject Eligibility

5.1 Number of Participants

We aim to enroll a total of 8-10 patients in this study at Stanford University.

5.2 Inclusion criteria

- Diagnosis of EBS
- Minimum EBDASI feet activity score of 2/10
- Healthy male or non-pregnant female
- Age ≥4 years old or older

- Ability to complete 7 study visits, each for approximately 30-60 minutes, including 3 scheduled phone calls within a 40-week period
- Anticipated life expectancy ≥ 52 weeks
- Males and females of childbearing potential should be using an effective means of contraception.
- Laboratory values within the range of normal unless the PI feels they are not clinically relevant.

5.3 Exclusion criteria

- Allergy to sirolimus or components of the vehicle ointment
- Pregnancy, breast feeding
- Prior history of liver disease
- Serious known concurrent medical illness or infection, which could potentially present a safety risk and/or prevent compliance with the requirements of the treatment program.
- Known immunodeficiency virus or syndrome including those with:
 - Acquired Immunodeficiency Syndrome (AIDS)
 - Human Immunodeficiency Virus (HIV)
 - Hepatitis B
- Prior history of grafting surgeries or other surgeries in the dermatologic treatment area
- History of significant condition in the dermatologic treatment area such as trauma or non-healing chronic wound, which could impair evaluation for the treatment of EBS.
- Use of other investigational drugs within 30 days of the screening visit and/or has not recovered from any side effects of prior investigational drugs or procedure in the affected area (e.g., a biopsy).
- Use of acitretin within the last 1 month
- Use of Roaccutane within last 3 months
- Botox injections to the feet within the last 6 months.
- Participant is planning extra physical activities within the next 3 months.
- Amputated foot

5.4 Withdrawal from the study

Participants must discontinue investigational medicinal product (IMP) and be withdrawn from the study for the following reasons:

- Participant withdraws consent
- Investigator request e.g. non-compliance with visits
- Participant meets any of the above exclusion criteria

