7.5 Prohibited concomitant medications

Participants may take other medications for treatment of the symptoms associated with EBS, so long as they do not fall into any of the prohibited medications category (see exclusion criteria).

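### Sections 5.4, 6.9 and 7.4 do not secure an end-of-treatment FHSQ from people who stop the ointment early, so one or both primary values may be lost

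*Combined protocol and SAP*

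**What the plan says.** Section 8.3 makes FHSQ foot function a primary outcome, measured as change from baseline at the close of each treatment. Section 6.1 puts those closes at Week 12 and Week 28. The Schedule of Events lists the FHSQ at Weeks 0, 4, 12, 16, 20, 28 and 32. It has no FHSQ at Week 40 and no early-termination column.

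Three places deal with stopping:

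- **Section 5.4:** "Participants must discontinue investigational medicinal product (IMP) and be withdrawn from the study for the following reasons". The reasons are withdrawn consent, investigator request (the example is not keeping visits) and "Participant meets any of the above exclusion criteria".
- **Section 6.9:** people who withdraw from treatment enter follow-up, which is Weeks 32 to 40 with a physician phone call at Week 40. It does not mention the Week 12 or Week 28 visit.
- **Section 7.4:** a participant unblinded during treatment leaves the treatment period and goes to follow-up.

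Some exclusion criteria in Section 5.3 can arise during the trial: "Allergy to sirolimus or components of the vehicle ointment", "Pregnancy, breast feeding" and "Serious known concurrent medical illness or infection, which could potentially present a safety risk". Section 8.5 separately requires discontinuation after a positive pregnancy test. Section 5.4 does not say which criteria apply only at screening. Section 9 names no model and no rule for missing values.

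**The concern.** The primary comparison needs an FHSQ at the end of sirolimus and at the end of placebo. Followed as written, Section 5.4 ends data collection on the day the ointment stops, even for someone willing to return for one more questionnaire. Section 7.4 points the same way after unblinding, and Section 6.9 leaves the matter open.

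In a crossover of 8 to 10 people, each participant is 10% to 12.5% of the data. Some reasons for stopping, such as ointment allergy, could be caused by treatment. The people lost could then differ from those who remain, and enrolling replacements does not repair that. A questionnaire that was not collected at the time cannot be recovered later.

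**Working it through.** **1. What a stopper may be left with.** This sets the Schedule of Events against the three stopping rules.

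| Ointment stopped | End-of-treatment FHSQ that may be missing | FHSQ that may exist |
|---|---|---|
| Phase 1, before Week 12 | Week 12 and Week 28 | Week 0, possibly Week 4 |
| From Week 12 to before Week 28 | Week 28 | Weeks 0 and 12, at most also Weeks 16 and 20 |

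Weeks 4, 16 and 20 are not end-of-treatment values. The Week 32 FHSQ follows a wash-out and is not one either, even if the stopper attends.

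**2. The plan's own sample size.** Section 9.2 gives a difference of 30%, an SD of 40%, 8 subjects, two-sided 5% and power above 0.8. It does not say whether 40% is the SD of the within-person difference. For a paired t-test:

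- noncentrality = difference × √n / SD of the difference, with n − 1 degrees of freedom
- power = probability that the noncentral t exceeds the two-sided 5% critical value in absolute size

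With SD 40 and n = 8, noncentrality = 30 × √8 / 40 = 2.121 and power is 0.449, so the claimed figure is not reproduced. Under that reading 16 pairs are needed (power 0.801). Power of 0.80 with 8 pairs requires an SD of the difference of 25.95%. That value is back-solved and is not in the documents. The mismatch is a separate matter, and both SDs are carried below.

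**3. Losing complete pairs.**

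| Complete pairs | Power, SD 40 | Power, SD 25.95 |
|---|---|---|
| 10 | 0.562 | 0.901 |
| 9 | 0.507 | 0.858 |
| 8 | 0.449 | 0.800 |
| 7 | 0.386 | 0.723 |

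**4. What using off-ointment values does to power.** Suppose 8 participants supply both values, and one who stopped shows no sirolimus-placebo difference. This is an illustrative assumption. It would fit, for example, someone who stops sirolimus early in Phase 3.

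- Mean contrast = (7 × 30 + 0) / 8 = 26.25%.
- SD 40: noncentrality = 26.25 × √8 / 40 = 1.856, power 0.361, against 0.386 for the 7 completers.
- SD 25.95: noncentrality = 26.25 × √8 / 25.95 = 2.861, power 0.691, against 0.723.
- Allowing for the extra spread this participant adds (400,000 simulated trials), power is about 0.34 and 0.63.

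The as-randomised estimate is therefore diluted and somewhat less powerful than the completer analysis.

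**The case against.** The strongest reply is that most of this is silence. Section 6.9 does not cancel any visit, and the Schedule of Events does not limit the Week 12 and Week 28 FHSQ to people still on ointment. A site could keep those visits. That stands for Section 6.9, which is why the point says a stopper *may* lack the values. It does not stand for Section 5.4, which orders withdrawal from the study, and it is weak for Section 7.4.

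Interim FHSQs are also a fair point. A repeated-measures analysis could use Week 4 or Week 20, so a stopper is not without data. But Section 9 specifies no such analysis, and those are not the primary values.

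This is a pilot, and part of the loss cannot be avoided: consent can always be withdrawn, and people removed for missing visits may not return. Enrolling 10 would leave 8 pairs after two losses. All of that stands, but none of it deals with selective loss.

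A reader might infer three stronger things that the documents do not support:

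- **Rescue treatment after a poor response ends participation.** Section 7.5 allows other EBS medicines "so long as they do not fall into any of the prohibited medications category (see exclusion criteria", and Section 5.3 lists "Use of acitretin within the last 1 month" and "Botox injections to the feet within the last 6 months". Getting from there to study withdrawal means reading look-back entry criteria as on-study rules, adding Section 5.4, and supposing that poor response prompts the medicine. That is a chain of inference. It is a reason to clarify the wording, not a demonstrated route of loss.
- **The result is biased by a known amount or in a known direction.** No stopping rate or stopper's response is given. An off-ointment value also does not reveal what the on-treatment contrast would have been, and using it could move the estimate further from an on-treatment mean.
- **Keeping stoppers raises power.** Step 4 of the working shows a small fall.

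**Conclusion.** The point holds as a fault in data collection. Section 5.4 states a rule that gives up obtainable primary values, Section 7.4 points the same way, Section 6.9 is silent, and nothing elsewhere supplies an FHSQ at stopping. The avoidable cases are investigator request, a newly met exclusion criterion and unblinding, together with any other stop under Section 6.9 if the visits are not kept.

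The only size that can be given is for precision. One lost pair of 8 costs about 0.06 of power (0.449 to 0.386) or 0.08 (0.800 to 0.723). Both figures assume a complete-pair t-test and a true difference of 30%, and the second also rests on the back-solved SD. Whether stopping is selective, how often it happens and which way it would push the result are unknown. The change should be made, but the text does not show that the trial's conclusion would be wrong without it.

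**What to change.** In Section 5.4, state that:

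- stopping the ointment is not withdrawal from the study unless consent is withdrawn;
- the FHSQ is completed when the ointment is stopped and, where the participant agrees, at the scheduled end-of-treatment visit of the current period (Week 12 or Week 28);
- values recorded off ointment or after unblinding are flagged;
- certain listed exclusion criteria apply only at screening, with the remainder applying throughout.

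Then bring Sections 6.9 and 7.4 into line with this. Report an as-randomised analysis that uses the off-ointment values beside the on-treatment one. Which of the two is primary is the sponsor's choice, and which events should stop treatment is for the investigators.

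The cost is protocol and consent wording plus one 19-question form at stopping, since the Week 12 and Week 28 visits are already scheduled. The downsides are some visit burden for people off ointment and the dilution and small loss of power in the as-randomised analysis. Someone who stops in Phase 1 and never starts the second treatment still does not form a complete pair. Their Week 12 value helps only an analysis that accepts single-period data.

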6.0 Study Design and Intervention

6.1 Study Design

This study is a prospective, double-blind, randomized, placebo-controlled crossover study at Stanford University School of Medicine, USA. It includes a 6-week screening period, followed by a 4 Phase Pilot Clinical Trial (see Table 2).

Screening: Up to 6 weeks

Phase 1: 12-week treatment period

Phase 2: 4-week wash-out period

Phase 3: 12-week treatment period

Phase 4: 4-week wash out period

Follow-up: 8 weeks after end-of-trial visit.

This research study is expected to take approximately 40 weeks. There will be 2 different parts of the study which the subject may receive for initial treatment period either (a) placebo (no drug) or (b) study drug for 12 weeks, during their enrollment in the 40-week study. After the initial 12-week period, there will be a washout period consisting of 4 weeks, before starting secondary treatment. During the secondary treatment period, a switch will occur and subject will receive either the (a) placebo (no drug) or (b) study drug depending on which treatment was received initially. At some time point during the 40-week study, at least both feet will receive study drug. There will also be a post-treatment visit at week 16 and week 32, with a post study phone call at Week 40. The end of treatment period will occur at Week 12 and Week 28, with the final in-person study visit occurring at week 32. Structured phone calls made by a physician will occur at Week 2, Week 14, Week 18, and Week 40.

The EBDASI feet score needs to be within 20% of baseline to progress to Phase 3. If subject's score does not meet this criteria the Phase 2 wash-out can be extended to 6 weeks.

Treatments are switched after Phase 2.

In-person study visits:

- Week 0 (screening/baseline)
- Week 4
- Week 12
- Week 16
- Week 20
- Week 28
- Week 32

Structured physician phone-call will be scheduled at:

- Week 2
- Week 14
- Week 18
- Week 40

6.2 Recruitment Process

EBS is a rare orphan disease and Stanford is one of several multidisciplinary clinics in the world that focuses on the treatment of EB. With a prevalence of 6-10 per million, there are roughly 3,200 patients in the United States. This study aims to enroll a total of 8-10 patients at Lucile Packard Children's Hospital Stanford. We cooperate with national and international networks of families, researchers, and physicians who care for children and adults with EB and plan to use these groups to recruit subjects for this study. In addition we will use our email listserv ([contact]) to inform our national communities that we are recruiting for this study. Patients have previously signed Consent Forms that have been approved by the Stanford ethics committee to be involved in these databases and contacted. Over 200 people are contained within these databases, 24 of which have EB with known EBS genetic KRT 5/14 mutation. We will access these databases to gain participant names, addresses, phone numbers and email addresses that we will use to invite them to participate in the study. Preference in enrolment will be given to participants in proximity to the study site and those with genetic KRT 5/14 mutations. Genetic testing is not a requirement for EBS diagnoses nor study enrollment. The mechanism of disease in EBS is well known as an autosomal dominant defect in keratin 5 or keratin 14. We will not be genotyping, the cost of genotyping is high at \$3-4k per subject. If genotyping is already known, this information will be utilized. Our recruitment methods will not involve material inducements. A telephone recruitment form has been submitted with this IRB request. Study personnel will not receive incentives for recruiting study participants or for any other purpose directly related to the study.

6.3 Compensation for participation

There will be no compensation for participation in this study but travel expenses may be reimbursed e.g. by using IPTAAS (Isolated Patients Travel and Accommodation Assistance Scheme).

6.4 Screening/Baseline Period

Before any study-specific interventions are performed, the appropriate written informed consent must be obtained for the trial and a separate consent for skin biopsy, which is an optional additional procedure.

To assess subject eligibility, all screening assessments as follows should be completed: eligibility criteria, medical history and physical exam, weight and height, demography, vital signs, concomitant medications, Epidermolysis Bullosa Diseases Activity Score (EBDASI), Quality of Life in Epidermolysis Bullosa (QOLEB), collection of blood for: metabolic panel, complete blood cell count with differential, urinalysis, lipid profile.

The participant will also be initiated in how to use the Fitbit and completion of daily diaries and the various different questionnaires to be used in the trial.

6.5 Treatment Period – Phase 1

Participants who meet all eligibility criteria will be randomized 1:1 to receive either topical sirolimus 2% or placebo ointment. The on-site Registered Nurse will teach the participant how to apply the ointment to both feet and will administer the first dose of IMP at week 0. Subsequent twice daily application of IMP to both feet will be performed by the participant, this will continue for 12 weeks.

6.6 Wash-Out Period – Phase 2

After completion of Phase 1 the participant will stop applying the IMP to the feet for a period of 4 weeks at which point their baseline activity will be assessed. If their EBDASI feet score is within 20% of baseline they can proceed to Phase 3.

6.7 Treatment Period – Phase 3

Participants who received topical sirolimus 2% during phase 1 will switch to placebo ointment and vice versa. Twice daily application of IMP will be continued by the participant for a further 12 weeks. The trial will remain double-blinded throughout.

6.8 Wash-Out Period – Phase 4

After completion of Phase 3 participants will enter a further 4-week wash-out period where they will stop applying the IMP to their feet. At the end of Phase 4 they will attend for their final end-of-trial physician visit.

6.9 Follow-up Period

Week 32-40 will be the follow-up period with a structured physician phone consultation at Week 40. Participants who withdraw from treatment will also enter the follow-up period.

7.0 Study Treatment

7.1 Investigational Product

Topical sirolimus 2% and placebo ointment will be made and supplied by PCCA compounding pharmacy. Placebo ointment will consist of vehicle only – i.e. all the same components as the topical sirolimus 2% ointment minus the active

ingredient. Both will have the same appearance, texture and odor and will be in a matching container or tube.

Tubes will contain vehicle or sirolimus 2% ointment in a 60 gram supply, the amount of topical for twice daily application over 2 weeks. We expect 360 grams for each phase of the treatment, 720 grams total with 360 grams intervention and 360 grams vehicle. Vehicle is an ointment plasticized base contained no water that provides at least 6 months sirolimus stability (Chemistry RX, [name] April 8 communication; PCCA plasticized base information provided in Section 16). 'A kit' describes two components in a plastic bag or cardboard box: (1) vehicle (placebo) or intervention (sirolimus 2%) ointment in 60 gram tubes and (2) our "Study Drug Application Kit Instructions' (provided in Section 16).

Contents of the label will be in accordance with all applicable regulatory requirements.

Study Drug Storage: The IP will be stored at room temperature in a dry place, away from direct sunlight.

At each physician visit the participant will be re-supplied with sufficient IMP until their next visit. The containers will also be weighed to monitor how much IMP is being used.

Patients will be instructed to wear gloves and change gloves between applications.

